Most of this experiment is hypothesis generating, but we can estimate a sample size based on a two measures, assuming $\alpha = 0.05$ and power = 80%. We aim to detect a change in pupil size of 1.0 mm because this is approximately what was reported in previous studies and what may begin to be clinically meaningful. We conservatively estimate a SD of change of 1.0. We also aim to detect a change in visual acuity of 0.1 logMAR, which is one line of visual acuity, a clinically meaningful change, with a standard deviation change of 0.2. The sample size required for pupil size is eight subjects and the sample size for visual acuity is 31 subjects. We will aim to enroll a sample sufficient to detect both the pupil size and visual acuity change. Assuming a 10% drop out rate, we estimate a sample size of 35, and we include five extra subjects who may be ineligible, for a total sample size of 40 subjects.

C. Measurement / Instrumentation

Manifest Refraction

This is a standard clinical procedure used to measure glasses prescriptions during clinical examinations. Cycloplegic autorefraction, the standard measure of eye prescription in many studies, is not necessary because we are not measuring the change in prescription over time.

Phoria

We will measure phoria at near in order to determine whether low concentration atropine affects how the two eyes work together. Modified Thorington is a more repeatable and less subjective method of measuring phoria than alternating cover test.

Visual Acuity

We will measure the high contrast (black letters) visual acuity at distance and near and the low contrast (grey letters) at distance using logMAR visual acuity charts and scoring on a letter basis. These measures of vision are standard protocols for vision research.

We will measure the pupil size with the NeuroOptics VIP-200 Pupillometer (NeuroOptics, Inc., Irvine, CA) in bright and dim light. For the dim light condition, the subject will stand with his or her back toward the wall-mounted visual acuity chart with the room lights off except for the incandescent lamp pointed straight down over the examination chair at the opposite end of the room. For the bright condition, the subject will stand with his or her back toward the wall-mounted visual acuity chart, and the visual acuity chart illumination should be turned on and be the same as when taking visual acuity measurements (approximately 75 – 120 cd/m² or 9.3-9.9 EV).

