A detailed target on a stick will be too near the eyes to read the letter. The stick will be pulled away from the subject until the subject reads the letter. The distance between the forehead and the stick will be measured to determine the ability to focus.

While wearing full vision correction, the prescription will be measured ten times while looking at distance target using the Grand Seiko WAM-5500 Binocular Autorefractor/Keratometer (AIT Industries, Bensenville, IL). A target will then be placed at 33 cm, and the subject will be told to keep the target clear while measuring the prescription five times. The prescription at distance will be subtracted from the prescription at near, and that result will be subtracted from 3.0 D, which is the focusing demand.

Reading Speed will be measured using the Rate of Reading Test. This test contains the same 15 simple words, repeated on each line and presented in random order. It is meant to serve as a test of reading speed pre- and post-intervention.

Subjects will view a card held at 40 cm. Flippers with +2.50 D lenses on one side and -2.50 D lenses on the other side will be placed in front of the subject, and the subject will report when the letters become clear. The lenses will be flipped, and the subject will again report when the print is clear. This will be continued for 1 minute, and the number of flips will be counted. This is a routine clinical measure of the ability to change focus from distance to near.

We will survey subjects about light sensitivity, drop comfort, likelihood of taking the drop to delay the onset of nearsightedness, vision symptoms, headaches, and comfort of the proparacaine eye drop and an artificial tear eye drop (for comparison of drop comfort to low concentration atropine). We will use the following format to collect survey data (using different questions and anchors as necessary):

1	2	3	4	5	6	7	8	9	10
Good									Perfect

We will measure the pressure in the eye using a Tonopen, a clinical measure that is performed during routine eye examinations. This requires a drop of 1% proparacaine in each eye to numb the eye. This drop is also used during routine eye examinations.

D. Detailed Study Procedures

Manifest Refraction

The examiner will measure glasses or perform retinoscopy to get a starting point for the refraction. The refraction will be performed using Jackson crossed cylinder, binocular blur balance, and maximum-plus-to-maximum-acuity to obtain the final refraction.

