Tell the subject you want him/her to read the random words on a page as quickly as possible without making any mistakes. If you make a mistake, just continue reading the card. You will read for one minute. I will tell you when to start and when to stop. Have the subject hold Test A at 40 cm. Tell the subject to begin and immediately begin the stop watch. Put a line through each mistake. Circle the last word read correctly and record the number of words read correctly. If more than five mistakes occurred, have the subject read for another minute and continue until the subject makes five or fewer mistakes.

Ability to Shift Focus

Subjects hold the near visual acuity card at 40 cm. Flippers with +2.00 D lenses on one side and –2.00 D lenses on the other side will be placed above the subject's eyes. Tell the subject to say "now" as soon as the letters on the card are clear after each flip of the lenses. This will be timed for one minute, and the number of cycles will be recorded. Begin with the +2.00 D lenses and measure binocularly.

Surveys

Subjects will be told to circle the number that corresponds to their perception that answers each question, noting the descriptions at each end of the numbers.

Pressure in the Eye

Place one drop of 1.0% proparacaine in each eye of the subject, and have him/her answer the three questions about eye comfort after receiving the drop. Place a sheath on the measurement tip of the Tonopen. Have the subject view a distant object while holding the eye open. Press the button on the Tonopen and wait until the green light turns on. Lightly tap the Tonopen on the cornea, until a final "beep" sounds. If the screen has a "95" in the bottom right corner, then the measure is valid and can be recorded. If anything else is displayed, repeat the procedure.

Compounding of the 0.01% Atropine

The drug will be compounded by the Central Ohio Compounding Pharmacy. They will dissolve 0.1 g atropine sulfate USP monohydrate powder in 1000 mL sterile water to a final concentration of 0.01%, and add Benzalkonium Chloride as preservative.

E. Internal Validity

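### Reading speed: with one named card, no practice minute and no control group, a practice gain could mask a slowdown, and the plan does not say which minute is analysed after a retake

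*Combined protocol and SAP*

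**What the plan says.** Reading speed is item 4 among the measures listed in section I. The hypothesis there is that pupil size will increase and that nothing else will change by a clinically meaningful amount.

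Section III.A describes one group measured before treatment and again after about a week of drops, each subject acting as his or her own control. Section III.C describes the Rate of Reading Test as fifteen simple words that recur on every line in shuffled order, and adds: "It is meant to serve as a test of reading speed pre- and post-intervention".

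The procedure in section III.D is written once, with no distinction between visits. It says "Have the subject hold Test A at 40 cm". The subject reads for one minute, the examiner strikes out mistakes and records the count of correct words, and then: "If more than five mistakes occurred, have the subject read for another minute and continue until the subject makes five or fewer mistakes".

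Section III.F plans paired t-tests or Wilcoxon signed-rank tests. No practice minute, alternate card or practice adjustment appears in any section. The text does not say which minute enters the analysis after a retake, or that error counts and number of attempts are kept as data.

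**The concern.** In an uncontrolled before-and-after comparison, the measured change is the drug effect plus everything else that differs between the visits. For a timed reading task, familiarity with the task is an obvious candidate, and it works against a slowdown. In a study of side effects the costly error is a false finding of no change. That is also the result the protocol expects, and section III.E offers the adult data as a worst case for children. Section III.E defends the pre-post format but does not mention repeat testing.

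The retake rule raises a second, smaller question. If a minute with more than five mistakes is replaced by a later one, the analysed score has been selected on accuracy, and accuracy is something near blur could affect.

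**Working it through.** **Inputs from the documents.** Table 2 reading speed: 3.36 ± 0.55 (Day 1), 3.16 ± 0.54 (Day 3) and 3.25 ± 0.45 (Day 5) words per second, p = 0.12. Sample size from section III.B: 31 for visual acuity, 35 after 10% dropout.

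**The plan's own sample sizes.** These use alpha 0.05 and 80% power; two-sided testing is assumed because sidedness is not stated. n = (SD × (1.960 + 0.842) / difference)².
- Pupil size ("We aim to detect a change in pupil size of 1.0 mm", SD of change 1.0): 2.802² = 7.85, so 8, as stated.
- Visual acuity (0.1 logMAR, SD of change 0.2): (0.2 × 2.802 / 0.1)² = 31.4, against 31 stated.
- Dropout: 31 / 0.9 = 34.4, so 35, as stated.

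There is no corresponding figure for reading speed, so the rest uses 31 completing subjects.

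**Size of a practice gain that would matter.** In words per minute, Table 2 is 201.6, 189.6 and 195.0.
- Day 3 fall: 201.6 − 189.6 = 12.0; 12.0 / 201.6 = 6.0%.
- Day 5 fall: 201.6 − 195.0 = 6.6; 6.6 / 201.6 = 3.3%.

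A practice gain of the same percentage of baseline cancels each fall exactly.

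**Effect on power.** The SD of change is not given. With SDs of 33 (0.55 × 60) and 27 (0.45 × 60) and an assumed correlation r, SD of change = √(33² + 27² − 2r × 33 × 27). This is 23.9 at r = 0.7 and 14.6 at r = 0.9. Power is for a two-sided paired t-test, n = 31, on the net change (true fall minus gain × 201.6).

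| True fall (words/min) | Assumed gain | Net fall | Power, r = 0.7 to 0.9 |
|---|---|---|---|
| 12.0 | 0% | 12.0 | 77% to 99% |
| 12.0 | 3% | 6.0 | 27% to 59% |
| 12.0 | 5% | 1.9 | 7% to 11% |
| 6.6 | 0% | 6.6 | 32% to 68% |
| 6.6 | 3% | 0.6 | about 5% |

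For the 6.6-word fall, a 5% gain reverses the sign: 6.6 − 10.1 = −3.5, an apparent improvement.

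**Retake rule.** No error rate is given, so this is a simulation under assumptions: Poisson errors, minute-to-minute SD 10 words, mean errors falling with each retry, true slowing of 6.6 words, and the last minute kept.
- Mean errors of 1 at both visits: about 0.1% of post-treatment tests need a retake, and the rule changes nothing.
- Mean errors rising from 1 to 5: about 38% need a retake. The first-minute change in correct words is −6.6 − (5 − 1) = −10.6.

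In the second case, the last-minute change depends on how subjects behave on a retake:

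| Speed on each retake | Last-minute change |
|---|---|
| 6 words faster | −6.2 |
| unchanged | −9.0 |
| 6 words slower | −11.7 |
| 12 words slower | −14.4 |

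The rule can therefore shrink or enlarge the measured fall.

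**The case against.** A reader might infer that the procedure does hide a drug-related slowdown, and that the card and the retake rule both push towards no change. The documents do not support that.

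- They show neither a practice gain nor an established slowdown. The Table 2 change has p = 0.12 and is not monotonic, and the reading test used in that study is not named. The 3% to 6% gain is chosen to match the falls it would cancel; it is not an estimate.
- The retake rule has no fixed direction. Subjects are told to avoid mistakes, so a retake may be slower. The rule also applies at baseline, where a retake that raises the kept score would enlarge a later fall.
- Blur-induced errors look unlikely on the protocol's own figures. Near acuity with 0.01% changed by −0.02 logMAR in Table 1 (children), and Table 2 gives 9.1 D of accommodation on Day 5 against a demand of 1 / 0.40 = 2.5 D at 40 cm.
- Use of Test A at both visits, and discarding of the failed minute, are inferences. Both are reasonable readings of a single procedure text, but neither is stated.
- An error ceiling has a purpose: it keeps accuracy roughly comparable, so that speeds can be compared.
- The study is mostly hypothesis generating and is not sized on reading speed.

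All of this stands, and it makes the retake rule the lesser issue. It does not answer the practice point. Shuffled words limit memorising but not familiarity with the task, and a practice gain needs no blur to operate.

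**Conclusion.** The point holds as a limit on interpretation. As written, the procedure cannot separate practice from drug effect, and a modest practice gain could mask a slowdown of the size in Table 2. How much power is lost depends on assumed values for the gain and the pre/post correlation. Even with no practice gain, 31 subjects give only 32% to 68% power for a 6.6-word fall, so a non-significant result would be weak evidence of no effect in any case.

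On the retake rule, the supportable defect is that the analysed minute is undefined and attempts are neither capped nor explicitly recorded. Whether this matters depends on an error rate that the documents do not give: the effect is negligible near one error per minute and could be several words in either direction near five.

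This is a change the sponsor should make because it is cheap and because analysis cannot remove a practice effect afterwards. It does not threaten the study's main comparisons.

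**What to change.** Amend section III.D, Reading Speed:

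1. Give one unscored practice minute before the baseline measurement.
2. Use a different word order at each visit, with the order alternated across subjects.
3. Name the first timed minute (words read correctly) as the analysed score at both visits, with the qualifying minute of five or fewer mistakes as a sensitivity analysis. This retains the error ceiling without letting it define the main result.
4. Record the error count and the number of attempts at each visit.

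The cost is about one extra minute per subject at baseline, a second card and a few edited sentences, with no extra subjects. First-minute scores will be somewhat noisier than scores held to an error ceiling. The practice minute and second card must be in place before baseline testing. They reduce practice effects but, without a control group, cannot be shown to remove them, so the report should still state that limitation.

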Side Effects of Atropine (SEA) Study

NCT03593044

November 23, 2021

Research Protocol
Side Effects of Atropine (SEA) Study
Version 1.0

I. Objectives

The purpose of this study is to determine whether there are any changes in subjective or objective measures of eye comfort or vision. Specifically, we will monitor for the following changes:

1. High contrast distance, high contrast near, and low contrast distance visual acuity
2. Pupil size
3. Ability to focus the eyes for near work
4. Reading speed
5. Subjective comfort and vision issues
6. Headaches
7. Intraocular pressure

We hypothesize that pupil size will increase significantly, but no other measures will change clinically meaningfully.

II. Background and Rationale

1.0% atropine is routinely used to dilate pupils and knock out the ability to focus the eyes to see close objects clearly, and it also slows the progression of nearsightedness. Many eye care practitioners are now using 0.01% atropine to slow the progression of nearsightedness because it slows the progression of nearsightedness by 60%¹ to 83%,² and it causes much fewer side effects than 1.0% atropine. One study compared myopia progression and side effects of 0.01%, 0.1%, and 0.5% atropine in children. While 0.5% atropine slowed myopia progression significantly more than 0.01% atropine, there were no other differences in myopia progression over two years, and there were fewer side effects with 0.01% atropine (Table 1), so many eye care practitioners now use 0.01% atropine to slow the progression of nearsightedness.

Table 1. Ocular changes after taking various concentrations of atropine.

	0.01%	0.1%	0.5%	p-value
Accommodative amplitude (D)	-4.6	-10.1	-11.8	<0.001
Pupil size in dim light(mm)	1.15	2.71	3.56	<0.001
Pupil size in bright light (mm)	0.75	2.24	3.11	<0.001
Distance visual acuity (logMAR)	-0.02	+0.01	-0.01	0.44
Near visual acuity (logMAR)	-0.02	+0.06	+0.25	<0.001
Asked for glasses to improve near vision (% yes)	6	61	70	<0.001

Another study examined the changes in visual function and symptoms of young adults while taking daily drops of 0.01% atropine for five days. Only pupil size and pupil response exhibited a significant change over that time period (Table 2).

Table 2. The change in vision function while taking 0.01% atropine for five days.

	Day 1	Day 3	Day 5	p-value
Distance VA (logMAR, OD)	-0.10 ± 0.10	-0.08 ± 0.07	-0.08 ± 0.05	0.55
Near point of accommodation (D)	10.2 ± 1.42	10.0 ± 1.39	9.1 ± 2.12	0.08

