We will measure the potential side effects of low concentration atropine in adults rather than children, although children will ultimately receive low concentration atropine for myopia control. We are not examining the effects in children because adults will give a more accurate description of the side effects they experience than children. Because children typically complain less about eye comfort and vision issues than adults,³ we strongly believe that we will obtain data that would be considered the worst case scenario for children.

We will use a pre- post-test format in order to examine the changes to be expected over a short period of time. The first week of experience will typically guide the likelihood of long-term commitment to the treatment.^{4,5} We therefore want to know how much administration of low concentration atropine will have on subjects' vision.

F. Data Analysis

We will perform repeated measures t-tests to determine whether there are significant changes over time for normally distributed variables and Wilcoxon signed-rank tests to determine whether there are significant changes over time for non-normally distributed variables.

IV. Bibliography

4. Lang JM. The use of a run-in to enhance compliance. *Stat Med*. 1990;9(1-2):87-93; discussion 93-85.

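### The plan does not say which pupil reading or which acuity chart decides the study, so the headline comparison can be chosen after the data are seen

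*Combined protocol and SAP*

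**What the plan says.** The analysis plan in section III.F is one sentence. Its first half reads "We will perform repeated measures t-tests to determine whether there are significant changes over time for normally distributed variables"; the second half assigns Wilcoxon signed-rank tests to variables that are not normally distributed. It gives no primary comparison, hierarchy, significance level or rule for multiple tests.

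The sample-size paragraph in section III.B begins "Most of this experiment is hypothesis generating, but we can estimate a sample size based on a two measures". It sets alpha at 0.05 and power at 80%, and continues "We aim to detect a change in pupil size of 1.0 mm" and "We conservatively estimate a SD of change of 1.0". It adds a 0.1 logMAR change in visual acuity with SD 0.2. No light condition and no chart is named.

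Section III.C has pupil size measured in bright and in dim light. On acuity it says: "We will measure the high contrast (black letters) visual acuity at distance and near and the low contrast (grey letters) at distance".

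Section I gives the hypothesis: "We hypothesize that pupil size will increase significantly, but no other measures will change clinically meaningfully".

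**The concern.** Two measures are powered, but they correspond to five readings: two for pupil size and three for acuity. Describing most of the experiment as hypothesis generating implies that some part is not, and the text never says which part. Section III.F then treats every variable alike.

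Two things are at stake. First, the report could lead with whichever light condition or chart gave the preferred answer, and a reader could not tell that this had happened. Second, if each measure is tested at 5% with no stated hierarchy, isolated significant changes are to be expected even where the drop does nothing, and the plan gives no rule for reading them. Analysts cannot repair either problem once the data are known.

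**Working it through.** **Inputs.** Alpha 0.05, power 80%, pupil change 1.0 mm with SD 1.0, acuity change 0.1 logMAR with SD 0.2, stated sample sizes 8 and 31, 10% dropout giving 35, and five extra giving 40 (all section III.B). Sidedness is not stated; two-sided is assumed because it reproduces the sample sizes.

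**The plan's own figures.** Paired normal approximation: n = (SD × (1.960 + 0.842) / change)².
- Pupil: (1.0 × 2.802 / 1.0)² = 7.85, so 8. This matches.
- Acuity: (0.2 × 2.802 / 0.1)² = 31.4, which the plan gives as 31.
- Dropout: 31 / 0.9 = 34.4, so 35; plus 5 = 40. This matches.
- One-sided testing would give 6.2 and 24.7, which do not match.

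The calculation supports one pupil contrast and one acuity contrast, each at 0.05. It makes no allowance for choosing among five.

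**False-positive chance.** Assume k paired t-tests at two-sided 0.05 and no true change in any of the k measures. If the tests are independent, the chance of at least one rejection is 1 − 0.95^k. For correlated measures it was simulated with equal correlation between measures. The documents give no correlations, so 0 to 0.8 is an assumed range. Results at 31 and 35 subjects agree closely.

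| Tests | k | Correlation 0 | 0.5 | 0.8 |
|---|---|---|---|---|
| Acuity charts | 3 | 14% | 13% | 10% |
| Objective non-pupil measures | 9 | 37% | 27% | 17% |
| The nine plus three survey items | 12 | 46% | 33% | 19% |

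The nine are the three acuities, focusing ability, lag, ability to shift focus, reading speed, phoria and eye pressure. Phoria is measured under section III.C but is not in the list in section I. The third row assumes one test each for light sensitivity, vision symptoms and headache, because the protocol does not give the number of survey items. Pupil tests are left out because the plan expects a real pupil effect.

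**Does the choice of light condition change the answer?** Table 1 in section II gives a 0.01% atropine change, in children, of 1.15 mm in dim light; the row "Pupil size in bright light (mm") gives 0.75 mm. With SD 1.0, exact paired-t power against zero for 0.75 mm is 98% at 31 subjects and 99% at 35. For 1.15 mm it is above 99.9% at both. Both readings would probably be significant in the same direction. What differs is the reported size, on either side of the 1.0 mm used for planning.

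**Significance against clinical meaning for acuity.** With SD 0.2, the smallest mean change that reaches p < 0.05 is t × 0.2 / √n.
- 31 subjects: 2.042 × 0.2 / √31 = 0.073 logMAR.
- 35 subjects: 2.032 × 0.2 / √35 = 0.069 logMAR.

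Both are below 0.1 logMAR, so a significant acuity change can be smaller than the plan's own clinically meaningful change.

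**Power cost of a fixed order.** The pupil step has exact paired-t power of 99.97% at 31 subjects and 99.99% at 35. Acuity power is 77% at 31 and 82% at 35. Acuity can lose at most 0.03 percentage points by coming second, so its power is unchanged in practice. By contrast, splitting alpha equally (0.025 each) by the same formula would need 39 subjects for acuity, 44 with dropout and 49 with the five extra.

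**The case against.** The strongest reply has four parts.

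- **The study is mostly hypothesis generating and small.** Unadjusted testing is defensible when looking for side effects, since adjustment could hide one. This stands, and it is why the proposed change leaves the exploratory p-values unadjusted. It does not say which readings are the exception.
- **Section I judges the non-pupil measures by clinical meaning.** A reader might infer that one false significant result would contradict the hypothesis. The text does not support that. If there is no true change, an observed mean acuity change as large as 0.1 logMAR has a chance of about 0.5% per chart at 31 subjects and 0.3% at 35. However, section III.F provides only significance tests and sets no rule for clinical meaning.
- **The pupil result is not in doubt.** A reader might count the pupil tests among the false positives, or infer that the two light conditions could give opposite verdicts. Neither holds. The plan and its Tables 1 and 2 point to a real pupil effect, either light condition would very probably be significant, and no pass or fail rule is set at 1.0 mm. The choice of light condition affects the size reported, not whether a change is declared.
- **A false positive is not likely in the sense of more than even odds.** This stands: the non-pupil figures stay below one half throughout the range.

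What remains is that the sized contrasts are not identified and that nothing in the text prevents identifying them after the fact.

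**Conclusion.** The point holds in this form: section III.F names no deciding comparison, and section III.B's 1.0 mm and 0.1 logMAR belong to no particular light condition or chart. The chance of at least one false significant change is about 10% to 14% across the acuity charts and about 17% to 37% across the nine objective non-pupil measures. These figures rest on three assumptions: alpha of 0.05 applies to section III.F, which states none; the drop has no true effect beyond the pupil; and correlations lie between 0 and 0.8. The more serious risk is selective choice of the headline reading, especially among the acuity charts. This should be corrected, but it does not invalidate the design or the sample size.

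**What to change.** In sections III.B and III.F:

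1. Name one pupil light condition and one acuity chart as the deciding contrasts, and state that 1.0 mm and 0.1 logMAR refer to them. Which ones is for the investigators to decide.
2. Test them in fixed order at two-sided 0.05, for example pupil size first and acuity only if pupil size is significant. This holds the family-wise error rate at 5% for the two.
3. Label the other light condition, the other two charts and all remaining measures exploratory.
4. Report every measure with its mean change, 95% confidence interval and unadjusted p-value, and state how many tests were done. Make no confirmatory claim from an isolated p < 0.05 among the exploratory measures.
5. Judge the absence of a clinically meaningful acuity change by whether the confidence interval excludes 0.1 logMAR, not by a non-significant test, which cannot show it.

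**Cost.** A few sentences, no new data and no extra subjects. The readings not named can no longer be reported as confirmatory. Acuity power stays at about 77% with 31 completers and 82% with 35. The section III.B figure of 35 already includes dropout, so 31 is the planned number. If there is truly no change, the same 77% and 82% are the chances that the interval excludes a loss of 0.1 logMAR. Excluding 0.1 in both directions has a chance of about 2 × 0.77 − 1 = 54% and 2 × 0.82 − 1 = 64%, so the wording should say which is meant.

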Pupil size (mm, OD)	5.51 ± 1.74	6.55 ± 1.12	6.82 ± 0.61	0.04
Pupil response	3.0 ± 0.0	2.8 ± 0.5	1.1 ± 0.9	<0.01
Reading speed (words per second)	3.36 ± 0.55	3.16 ± 0.54	3.25 ± 0.45	0.12
Near point of convergence (cm)	6.8 ± 2.4	7.0 ± 2.2	8.0 ± 3.2	0.25

We plan to examine a wider range of objective measures of visual function and symptoms than previous investigations, including investigate the changes in vision, pupil size, the ability to focus the eyes for near work, reading speed, comfort of the drops, subjective visual effects, presence and severity of headaches, and whether or not someone would be willing to take the drops long-term if they delayed the onset of nearsightedness.

III. Procedures

A. Research Design

This is a prospective cohort study in which we will compare pre-treatment measures to post-treatment measures after taking the treatment for approximately one week. The subjects will serve as their own controls. This will allow us to see the changes to be expected while taking the eye drop. Because the half-life of the drug is approximately 4 hours and maximum cycloplegia (eyes can't focus for near work) occurs in less than one hour, a longer period of time is not required.

B. Sample

We will examine adults between the ages of 21 and 30 years. We are not examining the effects in children because adults will give a more accurate description of the side effects they experience than children. Because children typically complain less about eye comfort and vision issues than adults,³ we strongly believe that we will obtain data that would be considered the worst case scenario for children. The specific entry criteria are listed in Table 3.

Table 3. Entry criteria

Age	21 to 30 years, inclusive
Accommodation	No known history of accommodative issues or therapy

All subjects in the age range specified with no known accommodative (focusing) issues will undergo consent and be enrolled.

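### III.F plans only significance tests, so a non-significant result cannot by itself support the hypothesis of no clinically meaningful change; a 95% CI for the mean change and a display of individual changes would be a cheap improvement.

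*Combined protocol and SAP*

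**What the plan says.** I. Objectives sets out to "determine whether there are any changes in subjective or objective measures of eye comfort or vision" and then states the expectation: "We hypothesize that pupil size will increase significantly, but no other measures will change clinically meaningfully". II. Background and Rationale adds "presence and severity of headaches" to the things to be examined.

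III.B Sample says "Most of this experiment is hypothesis generating" and bases the sample size on two measures. One is pupil size (1.0 mm, SD of change 1.0). For the other, "We also aim to detect a change in visual acuity of 0.1 logMAR", "with a standard deviation change of 0.2". It describes the acuity figure as clinically meaningful and arrives at 31 subjects, or 35 after allowing for 10% dropout.

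III.C introduces the surveys with "We will use the following format to collect survey data" and shows a 1-10 scale, noting that questions and anchors will differ by item. The headache items are not reproduced.

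III.F Data Analysis is the entire analysis plan: "We will perform repeated measures t-tests to determine whether there are significant changes over time for normally distributed variables", and Wilcoxon signed-rank tests for variables that are not normally distributed. Neither III.F nor any other section plans a confidence interval, a display of individual changes, or a count of affected subjects.

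**The concern.** The hypothesis has two halves, and the planned tests serve only the first. A paired test can show that pupil size increased. It cannot show that the other measures did not change by a meaningful amount, because p>0.05 is compatible both with a trivial mean change and with one as large as the plan's threshold. Only an interval tells these apart.

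There is a second, smaller gap. Both tests look for a shift of the whole group. In a side-effects study a reader will also want to know whether anyone had a marked rise in eye pressure or a new headache, and a test of the mean is nearly blind to an event in one or two subjects. Headache presence is a fact about each subject, yet no planned analysis reports it.

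What is at stake is the study's closing statement. If it rests on non-significance alone, it could claim more than the data exclude.

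**Working it through.** **Inputs from III.B:** alpha 0.05; power 80%; acuity change 0.1 logMAR; SD of change 0.2; n = 31, or 35 before dropout. **Assumptions:** two-sided testing (not stated, but it reproduces the plan's figures), the alternative SDs 0.15 and 0.1, and the number and size of harms in step 3.

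**1. The plan's own sample size.** n = [SD × (1.960 + 0.842) / change]².
- Pupil size: (1.0 × 2.802 / 1.0)² = 7.85, so 8, as stated.
- Acuity: (0.2 × 2.802 / 0.1)² = 31.4, stated as 31.
- Dropout: 31 / 0.9 = 34.4, so 35, as stated.

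**2. What a non-significant acuity result leaves open.** CI half-width = t(0.975, n−1) × SD / √n.
- n=31: 2.042 × 0.2 / √31 = 0.073.
- n=35: 2.032 × 0.2 / √35 = 0.069.

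The test is non-significant when the absolute mean change is below the half-width. The CI reaches ±0.1 when the absolute mean change is at least 0.1 minus the half-width: 0.027 for n=31 and 0.031 for n=35. Take no true change and hold the SD fixed. The standard errors are 0.2/√31 = 0.0359 and 0.2/√35 = 0.0338, so the probability that both conditions hold is:
- n=31: 2 × [Φ(2.042) − Φ(0.742)] = 0.417.
- n=35: 2 × [Φ(2.032) − Φ(0.926)] = 0.312.

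Simulation that lets the sample SD vary gives:

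| SD of change | n=31 | n=35 |
|---|---|---|
| 0.2 (plan) | 41% | 31% |
| 0.15 | 6.5% | 3.0% |
| 0.1 | near 0% | near 0% |

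At SD 0.2 with no true change, the CI lies wholly inside ±0.1 in 53.8% (n=31) or 63.9% (n=35) of trials.

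**3. Harm in a small minority.** Changes are simulated as normal with mean 0, with k subjects shifted by 1 to 5 SD. Rejection rates at two-sided 5%:
- k=2, n=31: t-test 5.5-8.8%, Wilcoxon 5.2-6.8%.
- k=2, n=35: t-test 5.4-8.8%, Wilcoxon 5.2-6.8%.
- k=2, heavy-tailed changes: 5.3-8.4%.
- k=3: about 7-18%. k=5: about 10-57%.

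The point therefore applies to small minorities only.

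**4. Headache, if only the harmed subjects change.** The exact two-sided signed-rank p with m one-way changes is 2 × 0.5^m: 0.50 for m=2, 0.063 for m=5, 0.031 for m=6. A t-test with m equal changes and the rest zero has t = √[m(n−1)/(n−m)]. At n=31 this gives p = 0.161 for m=2 and 0.043 for m=4. Neither test can reach significance with two affected subjects.

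**5. What counts can say.** With zero events the exact 95% upper limit is 1 − 0.025^(1/n): 11.2% for n=31 and 10.0% for n=35. For 2 of 31 the interval is 0.8-21.4%.

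**The case against.** The strongest reply is that nothing here is an error. The study is described as mostly hypothesis generating, III.E aims at the changes to be expected over a short period, and paired tests suit that group-level aim. III.F does not forbid intervals or individual data, and nothing says that non-significance will be read as no meaningful change. All of that stands, and it is why this is an improvement and not a defect. It does not remove the gap: the hypothesis is about meaningful change, and no planned output addresses it.

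The acuity figure is sensitive to the SD. Table 2 in II. Background gives between-subject acuity SDs of 0.10, 0.07 and 0.05 in young adults on this drug. If repeat readings are not negatively correlated (an assumption), the SD of change is at most about √(0.10² + 0.07²) = 0.122, and at n=31 the 41% falls to about 0.3%. That is a different sample, so it gives a range and does not replace the planning value. A reader might infer that the trial will leave acuity unresolved about four times in ten; the documents support that only near SD 0.2.

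The 5-9% figure follows from an assumed scenario, because any test of a mean is weak when about 6% of subjects shift. The documents give no rate or size of harm. A reader might infer that the planned tests are wrong, or that the study will miss its harms in general. Neither follows.

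The headache count is also limited. With an assumed independent 10% background at each visit and n=31, two harmed subjects give about 4.4 new against 2.6 resolved, compared with 2.8 and 2.8 without harm. At 30% it is 7.5 against 6.1, compared with 6.5 and 6.5. It is descriptive and no substitute for a control group.

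**Conclusion.** The point holds as a cheap improvement. III.F gives no basis for a statement that a measure did not change meaningfully. For acuity the shortfall is about 41% (n=31) or 31% (n=35) of no-change trials at the plan's SD of 0.2, about 7% or 3% at 0.15, and negligible at 0.1. That part rests on the plan's own threshold and sample size and on roughly normal changes. The second part, rejection in about 5-9% of trials, rests on the assumption that 2 of 31-35 subjects are harmed and the rest have no mean change.

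Two further inferences go beyond the documents. One is that a particular mmHg cut-off should define an eye-pressure event: the SD of pressure change is not given, so no cut-off can be justified from the text. The other is that counts of acuity losers are useless, or that moderate losses in one or two subjects cannot be seen. That depends on the SD. At SD 0.1 and n=31, with two losses of 0.3 logMAR, a 0.3 cut-off flags at least one subject in 76% of trials, against 4% with no harm.

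**What to change.** Add one paragraph to III.F:

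1. Report each measure taken before and after treatment with a 95% CI for the mean change, using the Hodges-Lehmann interval where the Wilcoxon test is used.
2. State that any conclusion of no clinically meaningful change refers to the mean and rests on that interval, not on p>0.05. For acuity, compare it with 0.1 logMAR.
3. Display individual changes, with the largest worsening beside the largest improvement.
4. Report the number with new or worse headache beside the number with resolved or milder headache, descriptively, with exact 95% CIs. Say in advance which survey answers count.
5. Note that zero events in 31-35 subjects does not exclude a rate of about 10-11%.

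The cost is a paragraph and a few table rows from data already collected, with no new subjects, visits or procedures. The downsides are real. Intervals may be wide. The favourable conclusion becomes harder to claim: at SD 0.2 with no true change, the acuity interval falls inside ±0.1 in only about 54-64% of trials, whereas the test is non-significant in 95%. Without a control group the individual summaries remain descriptive.
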